4.4.2.3 SAEs

4.4.2.3.1 Last Vaccination

Last vaccination before an SAE is derived from the last visit numbers provided in the clinical database and is calculated as follows:

- If an SAE has a non-missing visit number, the visit number should be used to determine the last vaccination before the SAE
- If the visit number is missing, then the start date should be used to determine the last vaccination before the SAE

4.4.2.3.2 Time of Onset

Time of onset will be computed using the same methodology than for unsolicited non-serious AEs described in [Section 4.4.2.2.4](#).

SAEs will be analyzed throughout the study using the following periods:

- Within 28 days after injection
- During the 2-year follow-up period (i.e., from 28 days after injection until the last subject contact)
- During the study (i.e., all SAEs occurred during the study)

An SAE with missing time of onset will be considered to have occurred after the vaccination indicated by the visit number, so will be included in these tables. SAEs collected after Visits 1, 2 or 3 with missing time of onset will be included the table of SAEs analyzed “within 28 days”, and SAEs collected after Visits 4, 5 or 6 with missing time of onset will be included in the table of SAEs analyzed “during the 2-year follow-up period”.

Note: SAEs that occurred before vaccination (negative time to onset) will not be included in analysis, but will be listed separately.

4.4.2.3.3 Duration

Duration will be computed using the same methodology than for unsolicited non-serious AEs described in [Section 4.4.2.2.5](#).

4.4.2.4 Other Safety Endpoints

4.4.2.4.1 Pregnancy

This information will not be included in the analysis, but will be listed separately as collected.

4.4.2.4.2 Action taken

The information will be summarized as collected, including missing observations. No derivation or imputation will be done.

4.4.2.4.3 Seriousness

The information will be summarized as collected. No derivation or imputation will be done.

4.4.2.4.4 Outcome

The information will be summarized as collected. No derivation or imputation will be done.

4.4.2.4.5 Causality

The information will be summarized as collected. Missing causality (relationship) will be handled as described in Section 5.3.2.2.

4.4.2.4.6 AEs Leading to Study Discontinuation

A flag is available in the clinical database for all AEs in order to identify AEs leading to discontinuation.

The items that are counted are:

- Disposition table: A subject who has, on the termination form, the reason for early termination “Serious Adverse Event” or “Other adverse event” is checked
- Safety overview table: A subject who has either on the termination form, the reason for early termination “Serious Adverse Event” or “Other adverse event” is checked or lists an AE on an AE page (unsolicited, or SAE) that has “Reaction Leading to Termination” or “Event Leading to Termination” or “Serious Adverse Event Leading to Termination” checked that is at least Grade 1 and is within the time period indicated
- System organ class (SOC)/PT frequency table: An event (unsolicited, or SAE) that has “Reaction Leading to Termination” or “Event Leading to Termination” or “Serious Adverse Event Leading to Termination” checked that is at least Grade 1 and is within the time period indicated

4.4.2.4.7 AESIs

The following serious AESIs (reported as SAEs) will be considered:

- Serious hypersensitivity/allergic reactions occurring in all subjects within 7 days after vaccination
- Serious viscerotropic disease occurring in all subjects within 30 days after vaccination
- Serious neurotropic disease occurring in all subjects within 30 days after vaccination

- Serious dengue disease requiring hospitalization^a occurring in all subjects at any time during the study

The following non-serious AESI will be considered:

- Hypersensitivity/allergic reactions occurring in all subjects within 7 days after vaccination.

4.4.2.4.8 WHO Criteria

The WHO criteria will be derived for virologically-confirmed dengue cases.

A dengue case will be considered as meeting the WHO criteria if it is at least Grade I.

The definition of dengue haemorrhagic fever (DHF) grade I, II, III, and IV will be consistent with the 1997 WHO definition:

- Clinical manifestations
 - a) Fever: acute onset, high (≥ 38 °C) and continuous, lasting 2 to 7 days
 - b) Any of the following hemorrhagic manifestations: a positive tourniquet test, petechiae, purpura, ecchymosis, epistaxis, gum bleeding, and hematemesis and/or melena
- Laboratory findings:
 - a) Thrombocytopenia (platelet count $\leq 100 \times 10^9$ /L)
 - b) Plasma leakage as shown by hemoconcentration (hematocrit increased by 20% or more) or pleural effusion (seen on chest X-ray) and/or ascites and/or hypoalbuminemia

The first two clinical criteria, plus thrombocytopenia and signs of plasma leakage are sufficient to establish a clinical diagnosis of DHF. Pleural effusion (seen on chest X-ray) and/or hypoalbuminemia provide supporting evidence of plasma leakage.

DHF will be graded as follows:

- Grade I: Fever accompanied by non-specific constitutional symptoms; the only hemorrhagic manifestation is a positive tourniquet test.
- Grade II: Spontaneous bleeding in addition to the manifestations of Grade I patients, usually in the form of skin and/or other hemorrhages.
- Grade III: Circulatory failure manifested by rapid and weak pulse, narrowing of pulse pressure (20 mmHg or less) or hypotension, with the presence of cold clammy skin and restlessness
- Grade IV: Profound shock with undetectable blood pressure and pulse

Dengue cases may also be classified, as post-hoc analysis, by alternative definitions if and when they are available.

^a A hospitalized subject is any subject admitted to hospital with bed attribution or any healthcare institution and requiring in-patient care.

4.4.3 Efficacy

Not applicable.

4.4.4 Derived Viremia Variable

The following viremia endpoints will be calculated for each subject:

Presence of detectable (\geq LLOD) or quantified (\geq LLOQ) viremia (Yes, No) for the non-serotype specific dengue (by dengue screen RT-PCR) in hospitalized suspected dengue cases during the study.

4.4.5 Derived Other Variables

4.4.5.1 Age for Demographics

The age of a subject on the day of first injection of CYD dengue vaccine in CYD28 is computed as follows:

$$\text{Age in years: (Date of V01 in CYD28 - Date of birth + 1) / 365.25}$$

4.4.5.2 Age group

The age group code (“9 to 17 years of age” or “18 to 45 years of age” on the day of first injection in CYD28) is a part of the subject number. Nevertheless subjects with a wrong identifier due to misclassification at the time of randomization will be considered in their real strata of age at the time of analysis, based on the age definition in [Section 4.4.5.1](#).

4.4.5.3 Duration of the Study

The duration of the study is computed in days as follows: Latest date of all subjects (termination date, last visit date, date of last contact) – earliest date of all subjects (date of visit V01) + 1.

4.4.5.4 Subject Duration

The duration of a subject participation in the study is computed as follows:

Maximum (Visit dates, Termination date, Follow-up date, Last contact date) – V01 date + 1.

5 Statistical Methods and Determination of Sample Size

The analysis will be performed under the responsibility of the Sponsor’s Biostatistics platform with the SAS software, version 9.2 or higher (SAS Institute, Cary, North Carolina, USA).

The results of the statistical analysis will be available in the final clinical study report (CSR).

For descriptive purposes, the following statistics will be presented:

Table 5.1: Descriptive statistics produced

Baseline characteristics and follow-up description	Categorical data	Number of subjects. Percentage of subjects.
	Continuous data	Mean, standard deviation, quartiles, minimum, and maximum.
Clinical safety results	Categorical data	Solicited reactions: Number and percentage (95% confidence interval [CI]) of subjects. Unsolicited AEs and SAEs: Number and percentage (95% CIs) of subjects, and number of events. Hospitalized virologically-confirmed dengue case: Number and percentage (95% CIs) of subjects
Immunogenicity results	Categorical data (cutoff)	Number and percentage (95% CIs) of subjects.
	Continuous data (titer / titer ratio)	Log10: Mean and standard deviation. Anti-Log10 (work on Log10 distribution, and anti-Log10 applied): Geometric mean, 95% CI of the geometric mean, quartiles, minimum, and maximum. Graphical representation by Reverse Cumulative Distribution Curve (RCDC).
CMI, Ab specificity and affinity maturation	Categorical data	Number and percentage of subjects above or equal to the LLOD, between some ranges of values and number and percentage (95% CIs) of responders subjects.
	Continuous data	Log10: Mean and standard deviation. Distribution: Geometric mean, 95% CI of the geometric mean, quartiles, minimum, and maximum of the corrected values

The CI for the single proportion will be calculated using the exact binomial method (Clopper-Pearson method, quoted by Newcombe (2), i.e., using the inverse of the beta integral with SAS®).

For immunogenicity, assuming that Log10 transformation of the titers / data follows a normal distribution, at first, the mean and the 95% CI will be calculated on Log10 (titers / data) using the usual calculation for normal distribution (using Student's t distribution with n-1 degree of freedom), then antilog transformations will be applied to the results of calculations, in order to provide geometric means (GMs) and their 95% CI.

GM is defined as follows:

$$GM = \left(\prod_{i=1}^n y_i \right)^{1/n} = 10^{\left(\frac{1}{n} \sum_{i=1}^n \log_{10}(y_i) \right)}$$

where (y_1, y_2, \dots, y_n) are the observed titers or other data where applicable for each subject. Rounding rules on descriptive statistics will follow the sanofi pasteur standard technical guideline ("Conventions for the Presentation of Descriptive Statistics").

5.1 Statistical Methods

5.1.1 Hypotheses and Statistical Methods for Primary Objective

If the number of evaluable subjects in Group 1 achieves 176 (i.e. per-protocol analysis set [PPAS] with valid immunogenicity titers) which would give 80.2% power for non-inferiority testing, the following statistical comparison will be performed for the primary objective. The primary hypothesis of non-inferiority will be tested on the PPAS and is to be confirmed using the full analysis set (FAS). If the number of evaluable subjects in Group 1 does not reach 176 for any serotype, hypotheses testing may not be performed for primary objective and the planned analyses may be descriptive for primary endpoints.

5.1.1.1 Hypotheses

Individual Hypotheses for Each Serotype to Demonstrate Non-inferiority:

A non-inferiority testing approach will be performed for each serotype specific endpoint to demonstrate the non-inferiority in terms of GMTRs for each subject, 28 days post injection, of a CYD dengue vaccine booster dose compared to the third CYD dengue vaccine dose in subjects from CYD28 trial.

Individual hypotheses for each serotype will be as follows:

$$H_0^i: GM(V_{Booster}^i / V_{PD3}^i) \leq 1/2$$

$$H_1^i: GM(V_{Booster}^i / V_{PD3}^i) > 1/2$$

Where $i = 1, 2, 3$ and 4; $V_{Booster}^i$ is the immunogenicity titer 28 days after the CYD dengue vaccine booster dose and V_{PD3}^i is the immunogenicity titer 28 days after the third CYD dose in CYD28 subjects.

Overall Hypothesis to Demonstrate Non-inferiority:

The overall null hypothesis can be stated as: for at least 1 serotype, the post-booster dose response (28 days after the CYD dengue vaccine booster dose) is inferior to the PD3 response (28 days after the third CYD dengue vaccine dose in CYD28 subjects)

$$H_0^G: \text{at least one } H_0^i \text{ not rejected}$$

$$H_1^G: \text{all } H_0^i \text{ are rejected}$$

5.1.1.2 Statistical Methods

A non-inferiority test will be performed using the 95% two sided CI of $GM(V_{Booster}/V_{PD3})$ for each serotype and the 95% CI will be calculated using paired t-test (2). Subjects with non-missing PD3 and post-booster dose titers will be included in this analysis.

For each serotype, the non-inferiority will be demonstrated if the lower limit of the two-sided 95% CI is greater than 1/2. If the null hypothesis is rejected, then the alternative hypothesis of non-inferiority will be supported. The overall null hypothesis will be rejected if the 4 individual null hypotheses are rejected simultaneously.

5.1.2 Hypotheses and Statistical Methods for Secondary Objectives

5.1.2.1 Hypotheses and Statistical Methods for the First Secondary Objective

5.1.2.1.1 Hypotheses

If non-inferiority will be demonstrated for the primary endpoint, then superiority hypotheses will be performed.

Individual Hypothesis for Each Serotype to Demonstrate Superiority:

A superiority hypotheses testing approach will be performed for each serotype to demonstrate the superiority, 28 days post-injection, of a CYD booster dose compared to the third CYD dose in subjects from CYD28 trial, in terms of GMTRs for each subject.

Individual hypotheses for each serotype will be as follows:

$$H_0^i: GM(V_{Booster}^i/V_{PD3}^i) \leq 1$$

$$H_1^i: GM(V_{Booster}^i/V_{PD3}^i) > 1$$

Where $i = 1, 2, 3$ and 4; $V_{Booster}^i$ is the immunogenicity titer 28 days after the CYD dengue vaccine booster dose and V_{PD3}^i is the immunogenicity titer 28 days after the third CYD dose in CYD28 subjects.

Overall Hypothesis to Demonstrate Superiority:

The overall null hypothesis can be stated as: for at least 1 serotype, the post-booster dose response (28 days after the CYD dengue vaccine booster injection) is not superior to the PD3 response (28 days after the third CYD dengue vaccine dose in CYD28 subjects)

$$H_0^G: \text{at least one } H_0^i \text{ not rejected}$$

$$H_1^G: \text{all } H_0^i \text{ are rejected}$$

5.1.2.1.2 Statistical Methods

A superiority test will be performed using the 95% two sided CI of $GM(V_{Booster}/V_{PD3})$ for each serotype; the 95% CI will be calculated using paired t-test. Subjects with non-missing PD3 and post-booster titer will be included in this analysis.

For each serotype, superiority will be demonstrated if the lower limit of the two-sided 95% CI is greater than 1. If the null hypothesis is rejected, then the alternative hypothesis of superiority will be supported.

The overall null hypothesis will be rejected if the 4 individual null hypotheses are rejected simultaneously.

5.1.2.2 Hypotheses and Statistical Methods for the Other Secondary Objectives

5.1.2.2.1 Hypotheses

There are no hypotheses. All of the analyses will be descriptive.

5.1.2.2.2 Statistical Methods

5.1.2.2.2.1 Immunogenicity

Response elicited by booster dose

The time point to be used for the descriptive comparisons to describe the immune response elicited by CYD dengue vaccine booster (Group 1) as compared to placebo among subjects who received 3 doses of CYD dengue vaccine in CYD28 trial will be immediately prior to and 28 days post-Booster administration. Immunogenicity will be assessed descriptively using the following parameters:

- GMTs against each serotype with the parental dengue virus strains at each available time point
- Geometric mean of the individual titers ratio (GMTRs) against each serotype with the parental dengue virus strains
- Number and percentage of subjects ≥ 10 (1/dil) against each dengue serotype with the parental dengue virus strains at each available time point
- Number and percentage of subjects ≥ 10 (1/dil) against at least 1, 2, 3, or 4 dengue serotypes with the parental dengue virus strains at each available time point
- Number and percentage of subjects \geq various titer thresholds (1/dil) for at least 1, 2, 3, or 4 serotypes with parental dengue virus strains at each available time point
- Distribution of titers against each of the 4 serotypes with parental dengue virus strains at each available time point and corresponding RCDC
- Seroconversion rates 28 days after the injection for each of the four parental dengue virus strain of CYD dengue vaccine.

Two sample t-test on the log₁₀ transformed titers will be used for 95% CI for the ratio of GMTs (difference between GMTs on log scale).

Ab persistence

- At baseline: the time points to be used for the descriptive comparisons to describe neutralizing Ab persistence will be D0 (immediately prior to booster or placebo injection) and 28 days after the third CYD dengue vaccine dose in CYD28 subjects.
- At 6 months, 1 year and 2 years: the time points to be used to describe neutralizing Ab persistence will be 6 months, 1 year and 2 years after the booster or placebo injection.

Immunogenicity will be assessed descriptively using the same statistical methods and parameters as above.

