2.3 Additional Objectives

Only for the additional immunological tests (AIT) subset

- 1) To describe dengue neutralizing Ab levels (exploration of the Ab response's kinetics), Ab specificity and affinity maturation post-booster or placebo injection
- 2) To describe cell mediated immunity (CMI) responses post-booster or placebo injection.

^a If the planned sample size is not achieved, the analysis may be descriptive.

In all subjects

- 3) To assess post-booster neutralizing Ab levels against each dengue virus serotype while controlling for baseline neutralizing Ab levels against each dengue virus serotype

3 Description of the Overall Trial Design and Plan

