5.1.3.2.2 Analysis adjusting for baseline neutralizing Ab levels

Analysis of covariance (ANCOVA) will be used to compare the post-booster mean response of neutralizing Ab levels against each dengue virus serotype of Groups 1 and 2 adjusting for the baseline neutralizing Ab levels against each dengue virus serotype based on the least squares means (LSMEANS).

For each serotype, the following model will be considered:

$$\text{Log}_{10} \text{ titer}_i = \text{log}_{10} \text{ baseline}_i + \text{group}_i$$

Where:

titer_i is the post-booster titer value for each subject

baseline_i is pre-booster titer value for each subject

group_i is Group 1 or Group 2 for each subject

Before applying the above ANCOVA model, the interaction between the pre-booster titer value and the group will be assessed using the following model:

$$\text{Log}_{10} \text{ titer}_i = \text{log}_{10} \text{ baseline}_i + \text{group}_i + \text{log}_{10} \text{ baseline}_i \times \text{group}_i$$

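### Baseline adjustment is not assigned to the 6-month, 1-year and 2-year booster/placebo GMT ratios, because the planned ANCOVA names no visit

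*SAP*

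**What the plan says.** **Persistence.** SAP 5.1.2.2.2.1 sets the time points ("neutralizing Ab persistence will be 6 months, 1 year and 2 years after the booster or placebo injection") and then gives the method: "Immunogenicity will be assessed descriptively using the same statistical methods and parameters as above". Protocol 12.1.2.2.1 does the same. The preceding text contains one between-group method, a two-sample t-test in which log10 "transformed titers will be used for 95% CI for the ratio of GMTs (difference between GMTs on log scale"), with no covariate. It also lists a within-subject parameter, "Geometric mean of the individual titers ratio (GMTRs) against each serotype with the parental dengue virus strains", without saying which time points it covers after Day 28. SAP 5.2.5 puts the persistence analysis on the FAS. SAP 5.1.2.2.1 gives its status: "There are no hypotheses. All of the analyses will be descriptive".

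**Baseline adjustment.** The third additional objective (SAP 2.3) is "To assess post-booster neutralizing Ab levels against each dengue virus serotype while controlling for baseline neutralizing Ab levels". SAP 5.1.3.2.2 implements it by ANCOVA, "adjusting for the baseline neutralizing Ab levels against each dengue virus serotype based on the least squares means", after a check of the baseline-by-group interaction. The response "is the post-booster titer value for each subject"; no visit is given. Protocol 12.1.3 left the details of the model to the SAP, and the matching endpoint (SAP 4.3.1.1, item 4) names no visit either.

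**The concern.** The Day 0 titer is scheduled for every subject and is a natural covariate for later titers. Randomization is stratified by site and age group only (Protocol 6.5), so Day 0 titers are balanced by chance alone, and the comparison group is small (59 evaluable placebo subjects anticipated). Yet the section that governs the late visits leads to an unadjusted interval, and the section that adjusts does not say that it covers those visits.

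Two things are at stake. The first is the precision of the booster/placebo ratio at 6 months, 1 year and 2 years, which will be read as the durability of the booster. The second is when the choice is made. Under SAP 5.4 the trial statistician breaks the blind after the Day 28 lock. If the ANCOVA visits are still open then, whether to adjust the late results can be decided with the Day 0 imbalance already known.

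**Working it through.** **Inputs from the documents** (SAP 5.5): 176 and 59 evaluable subjects; log10 SDs after dose 3 (sd1) of 0.77, 0.74, 0.59 and 0.53 for serotypes 1 to 4, with sd2 twice sd1; correlation 0.6 between the post-dose-3 and post-booster titers.

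**Inputs assumed.** The documents give no Day 0 SD, no follow-up SD and no Day 0-to-follow-up correlation. I use sd1 for the Day 0 SD, sd1 or twice sd1 for the follow-up SD, and correlations rho of 0.3, 0.6 and 0.8. The plan's 0.6 belongs to a different pair of visits.

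**The plan's own figure.** No precision is stated for the persistence ratio. The one power figure reproduces and confirms the reading of the inputs. SDdiff = sqrt(sd1² + sd2² − 2 × 0.6 × sd1 × sd2), which is 1.242 for serotype 1. With n = 176, margin log10(2), one-sided 0.025 and a true ratio of 1, power is 0.892, 0.914, 0.987 and 0.996, overall 0.802 as stated. The printed 0.970 for serotype 3 does not fit: the four printed values multiply to 0.788. That does not affect this point.

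**Chance imbalance at Day 0.**
- SE = SD × sqrt(1/176 + 1/59) = SD × 0.1504.
- Serotype 1: 0.77 × 0.1504 = 0.116; 95% range 10^(1.96 × 0.116) = 1.69-fold either way.
- Serotype 4: 0.53 × 0.1504 = 0.080; 1.43-fold either way.
- Serotypes 2 and 3 lie between, at 1.65 and 1.49.
- With all 195 and 65 subjects, the range is 1.41 to 1.64.

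**Share carried to a later visit.** Slope = rho × SDfollow-up / SDbaseline.

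**Gain from adjustment.** SE(ANCOVA) = SE(unadjusted) × sqrt(1 − rho²).

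**Coverage of the unadjusted 95% interval given a Day 0 imbalance of 1.96 SE.** In units of the unadjusted SE the estimate has mean shift 1.96 × rho and variance 1 − rho².

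Serotype 1, follow-up SD 0.77, 176 vs 59 (unadjusted 95% limits ×/÷1.69):

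| rho | 1.69-fold Day 0 imbalance becomes | CI width factor | Adjusted limits | Unadjusted coverage given that imbalance |
|---|---|---|---|---|
| 0.3 | 1.17 | 0.95 | ×/÷1.65 | 92% |
| 0.6 | 1.37 | 0.80 | ×/÷1.52 | 84% |
| 0.8 | 1.52 | 0.60 | ×/÷1.37 | 74% |

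With a follow-up SD of 1.54 and rho 0.6, the slope is 1.2, a 1.69-fold imbalance becomes 1.87-fold, and the limits go from ×/÷2.84 to ×/÷2.31. Averaged over all randomizations, the unadjusted interval keeps about 95% coverage.

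**Do the GMTRs already do this?** Only partly. Relative to the unadjusted comparison with equal SDs, a change score has variance 2(1 − rho) and ANCOVA 1 − rho²: 0.80 against 0.64 at rho 0.6, and 1.40 against 0.91 at rho 0.3. In addition, SAP 4.4.1.1 sets a titer below the LLOQ of 10 to 5 in a numerator but 10 in a denominator. A placebo subject below the LLOQ at both visits therefore gets 5/10 = 0.5, an apparent halving without any change.

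**The case against.** The strongest reply is that this is an acceptable choice for a descriptive objective. Secondary objective 4 only describes persistence, no test depends on it, and a reader who takes it to ask whether the booster leaves higher titers goes beyond its wording. Randomization makes the unadjusted ratio unbiased, and its interval already allows for chance imbalance. All of this stands, and it limits the point to efficiency and to accuracy given the observed imbalance.

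A reader might also infer that the SAP rules out adjustment at the late visits because post-booster means Day 28. The documents do not support that. SAP 4.4.1.2 and 4.4.1.3 use the term without a visit. The Day 28 link comes from endpoints 3 and 4 in SAP 4.2.1.1, while endpoint 6 there uses the term for 6 months to 2 years, and the CMI responder rule in SAP 5.1.3.2.1 applies it to Day 28 and Month 12. What can be said is that the visit is unspecified.

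Other baseline information is planned: GMTs at each time point, Day 0 included, will make an imbalance visible, and SAP 5.1.4 adds analyses by pre-booster dengue status. Neither is an adjusted booster/placebo estimate at the late visits.

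Finally, adjustment has a cost. Protocol 5.1.4 (Visit 1) allows injection without a Day 0 sample, and the FAS requires only post-injection serology, so such subjects leave the adjusted model. If the Day 0 slope differs between vaccinated and placebo subjects, one common-slope ratio is not a clean summary and sqrt(1 − rho²) is only approximate. This is a reason to report both estimates, not to leave the visits open.

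**Conclusion.** The point holds as a gap in assignment: an unadjusted interval is specified for the persistence visits, and the planned baseline-adjusted model is not tied to them. The size is moderate. Under the assumed SDs a chance Day 0 difference of up to about 1.4- to 1.7-fold is plausible, and adjustment would narrow the log-scale interval by about 5% to 40%, or 20% at a correlation of 0.6. These figures are illustrations, since the Day 0 SD, the follow-up SD and the correlation are not in the documents, and fewer subjects may have samples at 2 years.

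It would be wrong to conclude that baseline imbalance passes in full into the persistence result, or that the result is biased. The share carried is the Day 0 slope: 0.3 to 0.8 with equal SDs, and above 1 only if the follow-up SD is sufficiently larger than the Day 0 SD. No trial conclusion rests on this analysis. Naming the visits is still worthwhile, because it uses data already scheduled and a model already planned.

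**What to change.** In SAP 5.1.3.2.2, state that the ANCOVA with log10 Day 0 titer is fitted for each serotype at Day 28, 6 months, 1 year and 2 years, with the planned baseline-by-group interaction check at each visit and the FAS for the three persistence visits. Report the back-transformed adjusted GMT ratio with its 95% CI beside the unadjusted GMTs and ratio, not in place of them. State how many subjects drop out for lack of a Day 0 titer, and how the result will be presented if the slopes differ. Add a cross-reference in SAP 5.1.2.2.2.1, and settle the wording before the Day 28 unblinding.

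The cost is a few lines of SAP text and three further runs of a planned model per serotype, with no new data.
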